For **Phase 6**, we will have two sets of analyses. For Phase 6a, we will conduct Generalized Estimating Equation models with main effects (Study arm, time) and interaction terms (study arm*time) for all outcomes, except for civic engagement intention, which was not measured at multiple time points. Based on power analyses to estimate the minimal detectable effect size for study arm differences among 100 Latinas (assuming maximum attrition, given current attrition rates) across nested surveys (ICC = 0.0-0.5), $p < .05$, power=0.80, and two-tailed tests, we would be able to detect a medium-sized effect for a study arm*time interaction effect. For civic engagement intention, we will conduct a logistic regression. We will cluster by cohort/group and adjust for demographic covariates in all models. For Phase 6b, we will assess the: 1) number and types of civic engagement and community development activities; 2) number of women who indicate interest; and, 3) number of women who attend. Secondary analyses include: 1)

describing the number and types of barriers to participation; and, 2) characterizing predictors to participation via bivariate regressions.

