We will be conducting educational classes at the two participating sites. We will also administer several surveys at different sessions. The variations in the implementation of Phase 3 will be the Workshops at each site. Each site will conduct a Breast Cancer Education session. However, TRP will conduct Communication and Volunteerism workshops, whereas Juan Diego will conduct Diet and Physical Activity workshops. The Intervention is broken down into 3 sessions at each site across 3 consecutive weeks. Each session will be held with 5-8 recruited participants. We will hold 5 – 9 sessions at each participating site for three consecutive weeks.

Ancillary studies and analytic studies include: 1) qualitative data collection with participants' family and friends (Phase 4); 2) cost data collection and cost-effectiveness analysis (Phase 5); and, 3) community volunteerism data abstraction (e.g., preferences regarding events; number of contacts; barriers, if any, during contact; decisions/solutions made, if any during contact; interest in event participation; type of event; and attendance at event) and secondary analysis of Phase 3 volunteerism data (Phase 6). During Phase 7, 20 former intervention participants will participate in focus groups to provide their perspectives on their experiences and suggestions for future interventions.

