3.0 Objectives/Aims

The primary goal of this proposed work is to develop materials and conduct a trial that would examine the relative efficacy of education and empowerment interventions to improve breast cancer screening among Chicago-based Latinas. With regard to our objectives, we proposed to:

Aim 1: Develop and compare the efficacy of a breast health empowerment intervention on guideline-concordant screening compared to an education intervention, using an area-level treatment control group design with a community-based sample of 150 Latinas. The empowerment arm will include breast health and empowerment information (e.g., how to begin conversations, where to volunteer). The education arm will include only breast health information. Content draws from my team's existing materials. Hypothesis: Empowerment participants will have increased screening compared to education participants.

Aim 2: Compare interventions' effects on psychosocial facilitators of screening across six months. Hypothesis: Empowerment participants will have sustained increases in self-reported self-efficacy, norms, support, and knowledge about breast cancer screening compared to education participants.

Aim 3: Compare interventions' network effects through egocentric network analysis. Hypothesis: Empowerment participants will have greater social connectedness related to breast health and network size and will have referred a greater number of peers to participate in the study compared to education participants.

Aim 4: Characterize intervention effects on family and friends of intervention participants.

Aim 5: a) Determine the incremental costs for each additional woman screened for the empowerment approach relative to the education approach, combining new cost data with existing effect measures in our trial. Hypothesis: The empowerment intervention will have low incremental costs for each additional woman screened, especially when including indirect effects. b) Use those data and published literature to compare approaches in terms of achieving HP2020 goals and costs for additional life-years gained across 10 years, using existing simulation platforms. Hypothesis: The empowerment intervention will be more cost-effective than the education intervention in terms of life years gained.

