Aim 6: a) quantify the relative effects of education and empowerment interventions on intention to volunteer, volunteerism behaviors, intention to participate in civic engagement, and civic engagement behaviors; and, b) characterize the feasibility of a community-based civic engagement and community development navigation program for Latinas.

Aim 7: Characterize the perspectives and experiences of intervention participants, based on focus groups (n=20).

Toward that goal, we will first run semi-structured focus groups with 20 Latinas who will not be eligible for the future trial and 10-15 CHW/CHV/promotoras who would be eligible to deliver the intervention in order to: 1) identify relevant topics to incorporate into interventions; and 2) examine circumstances that may facilitate implementation. No contact information on women who have participated in any previous focus groups or will we re-contact any woman who has already participated in a focus group for future trial. We will only invite new recruits for each focus group that is held. This phase of the project will be called Phase 1.

We will then create materials based on this feedback and consultation from the UIC CCTS Community Engagement Advisory Board.

Next, we will run semi-structured focus groups with a second set of 20 Latinas who would be eligible for the future trial and 10-15 CHW/CHV/promotoras who would be eligible to deliver the intervention in order to 1) verify the appropriateness and logic of the updated material; and 2) identify alternative content areas and approaches. This phase of the project will be called Phase 2.

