Costs will be incorporated across 10 years and be dependent on individuals' behaviors and state (e.g., costs for women with 1 false-positive event include provider visit, screening, and diagnostic care; for women with a definitive cancer diagnosis, includes all costs, including those for subsequent surveillance screening). The following beginning list includes assumptions and rules we will make for the model: 1) guideline-concordant screening is defined as obtaining a mammogram every 2 years for women aged 50-74 years old; 2) screening occurs between 2010 and 2020; 3) screening, staging, and mortality rates for future years (e.g., 2018-2020) are estimated based on population-level trends and 2010-2017 rates; 4) expected changes to stage distribution of breast cancer are based on program effect estimates; 5) a discount rate of 0.03 is used; and, 6) cost data will be standardized to 2017 US dollars. Each run will be programmed to provide the following outputs per year for 10 years: 1) cumulative net costs; 2) breast cancer screening; 3) stage distribution; and, 4) age-adjusted mortality rates.

Phase 6

Phase 6 will only include survey data (Phase 6a) and community study records for Phase 3 participants who agree to have their data released to UIC (Phase 6b). Phase 3 will not be asked for any additional data. We are requesting a waiver of documentation and alteration for Phase 6. This requested waiver will not adversely affect the rights and welfare of subjects and is the only way for study staff to obtain objective data regarding subjects' participation in community volunteerism.

For Phase 6a, we will conduct secondary analyses regarding study arm differences in Phase 3 survey data (T1, T2, T3) regarding community volunteerism, including volunteerism intention, civic engagement intention, volunteerism behaviors, and civic engagement behaviors. We will use multiple imputation techniques to handle missing data. For analyses, we will conduct Generalized Estimating Equation models with main effects (Study arm, time) and interaction terms (study arm*time) for all outcomes, except for civic engagement intention, which was not measured at multiple time points. Based on power analyses to estimate the minimal detectable effect size for study arm differences among 100 Latinas (assuming maximum attrition, given current attrition rates) across nested surveys (ICC = 0.0-0.5), $p < .05$, power=0.80, and two-

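### Civic engagement intention is compared between arms at one unspecified survey, adjusting only for demographics, although each arm is a single site; the arm odds ratio cannot be read as an intervention effect

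*Combined protocol and SAP*

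**What the plan says.** Aim 6a (Section 3.0) undertakes to "quantify the relative effects of education and empowerment interventions on intention to volunteer, volunteerism behaviors, intention to participate in civic engagement, and civic engagement behaviors". Section 6.2 (Phase 6) names the source as "Phase 3 survey data (T1, T2, T3) regarding community volunteerism, including volunteerism intention, civic engagement intention, volunteerism behaviors, and civic engagement behaviors".

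Section 9.0 (Phase 6) plans generalized estimating equations with arm, time and arm-by-time terms "for all outcomes, except for civic engagement intention, which was not measured at multiple time points". For the excepted outcome it says: "For civic engagement intention, we will conduct a logistic regression". The adjustment rule is: "We will cluster by cohort/group and adjust for demographic covariates in all models". Sections 6.2 and 6.4 repeat the same text.

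On design, Aim 1 describes the trial as "using an area-level treatment control group design with a community-based sample of 150 Latinas". Section 1.0 ties content to place: "TRP will conduct Communication and Volunteerism workshops, whereas Juan Diego will conduct Diet and Physical Activity workshops". Section 6.1 (Recruitment, Phase 3) states convenience sampling, 75 women from each organisation. No randomisation is described.

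**The concern.** Arm and site are the same variable. An outcome with a pre-intervention reading can be compared as change, so a stable difference between the two organisations' clients cancels out of the arm-by-time term. An outcome read once offers no such protection, and the arm coefficient absorbs whatever already distinguished the two groups of women, apart from what the covariates explain.

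A prior difference is plausible for this outcome. Section 6.2 (Phase 6) says that both organisations recruited the participants and run programs through which clients become involved in their communities, so civic orientation may differ between the two client groups. The named covariates are demographic and do not measure that orientation.

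At stake is one claim under Aim 6a. It would appear beside three outcomes analysed over time, with nothing in the plan requiring a note that it rests on weaker evidence. The error could run either way: a prior difference favouring the empowerment site would mimic a benefit, and one favouring the education site would hide a benefit.

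**Working it through.** **1. The plan's own figure.** The only Phase 6a power statement is a verbal medium effect for the arm-by-time interaction, with 100 women, ICC 0.0-0.5, two-sided 0.05 and power 0.80. As a difference in change between two surveys, with 50 women per arm, the detectable effect is d = (1.960 + 0.842) × √[4(1 − ICC)/50]:

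- ICC 0: 2.802 × √0.08 = 0.79
- ICC 0.5: 2.802 × √0.04 = 0.56

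The plan gives no number to match, and the statement does not cover civic engagement intention. For a single-time-point comparison of 50 with 50, the detectable odds ratio is about 3.1-3.4 at assumed base rates of 20-50%, and about 4.4 at 10%.

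**2. What each possible survey implies.**

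| Item asked at | What the arm odds ratio contains |
|---|---|
| T1 (before Session 1) | Prior site difference only |
| T2 (after Session 3) or T3 (six months later) | Intervention effect plus any prior site difference not explained by demographics |

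Under neither reading does the planned regression isolate an intervention effect.

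**3. Whether other parts of the plan help.**

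- Clustering by cohort or group: every group lies within one site, so this changes the standard error and leaves the confounding.
- Section 9.0's wider covariate rule, which considers pre-study factors, is written for the Phase 3 screening outcome. It is explicitly carried over to the psychosocial and network outcomes. The Phase 6 text does not carry it over and names demographics instead.
- Section 4.1a excludes women with a history of health volunteering. That narrows one kind of prior engagement but does not cover civic engagement.

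**4. Illustrative bias.** The documents give no site difference and no rates, so all inputs here are assumed: no true effect; prior intention z with unit SD, higher by d = 0.3 or 0.5 SD at one site; logit P(yes) = z − d/2; demographics explaining none of d. Averaging over z gives:

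- d = 0.3: 46.9% v 53.1%, OR = (0.531/0.469)² = 1.28
- d = 0.5: 44.9% v 55.1%, OR = (0.5515/0.4485)² = 1.51

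If the shift favours the other site, these become 1/1.28 = 0.78 and 1/1.51 = 0.66.

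Now add a T1 proxy correlated r with z, whose own site difference is r·d. Adjustment leaves a site difference of d(1 − r²):

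| d | r | Remaining shift (SD) | Simulated OR |
|---|---|---|---|
| 0.3 | 0.5 | 0.3 × 0.75 = 0.225 | 1.21 |
| 0.3 | 0.7 | 0.3 × 0.51 = 0.153 | 1.15 |
| 0.5 | 0.5 | 0.5 × 0.75 = 0.375 | 1.38 |
| 0.5 | 0.7 | 0.5 × 0.51 = 0.255 | 1.26 |

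**5. Chance of a false finding.** This uses a pooled two-proportion test with 50 per arm, no true effect and an assumed base rate of 30-50%:

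| Prior site OR left after adjustment | P(p < 0.05) |
|---|---|
| 1.0 | 5% |
| 1.5 | 16-17% |
| 2.0 | 38-39% |

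For example, at a base rate of 30% an OR of 1.5 gives 39.1% at the other site. The null standard error is √(2 × 0.3455 × 0.6545/50) = 0.0951 and the alternative one is 0.0947. The upper-tail z is (1.96 × 0.0951 − 0.091)/0.0947 ≈ 1.00, and the two tails together give 0.159.

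**The case against.** Four points on the other side deserve weight.

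- **Timing.** A reader might infer that the item has no baseline and was read only after the intervention. The documents say only that it was not measured at multiple time points, and no passage names the survey. That stronger statement is unsupported, although the conclusion holds whichever survey it was.
- **Available T1 covariates.** A reader might infer that T1 holds volunteerism intention and civic engagement behaviors as well as past volunteering. Section 6.2 (Phase 3) lists only volunteerism history, with social interactions, beliefs, demographics and screening variables. Section 6.2 (Phase 6) names the three surveys together without assigning outcomes to them, so the other two measures at T1 are plausible but unconfirmed. The exclusion of prior health volunteers may also weaken volunteerism history as a proxy, so correlations of 0.5-0.7 may be optimistic for it.
- **Size.** The 1.28-1.51 range comes from a model without demographics. It describes the planned model only if demographics explain none of the assumed site difference. No document supports the size or direction of that difference.
- **Stakes.** Sections 6.2 and 6.4 call Phase 6a secondary analysis of study arm differences, and Section 12.1 calls Phase 6 a pilot study. Aim 1 screening is not touched. Confounding of arm with site affects the whole trial, and the added covariates would remove only part of it here.

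These points limit how much can be claimed and lower the importance. None of them makes the single-time-point arm odds ratio an estimate of the intervention's effect.

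**Conclusion.** The concern holds in a conditional form. Arm equals site in a non-randomised convenience sample, the outcome is read once, and only demographic covariates are named. Any prior site difference in civic orientation that those covariates do not explain would therefore pass into an odds ratio that Aim 6a presents as a relative effect.

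The documents do not show that such a difference exists, so it would go too far to say that bias will occur. The figures in the working are illustrations and rest on the assumptions listed there.

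The arm-by-time outcomes are better protected if they have a T1 reading, but only against stable site differences and not against differing trends. Importance is low to moderate.

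**What to change.** In the Phase 6a text of Sections 6.2, 6.4 and 9.0:

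1. State which survey supplies civic engagement intention.
2. If it is T2 or T3, add T1 volunteerism history to the logistic model as a prespecified covariate. Add volunteerism intention and civic engagement behaviors too, where the T1 instrument confirms that they were collected.
3. If it is T1, do not report the item as an intervention outcome; it can only describe the sites before the intervention.

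In Aim 6a, describe a T2 or T3 result as an adjusted between-site difference at one time point, acknowledge residual site confounding, and rest effect statements on the repeatedly measured outcomes.

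The cost is a check of the survey instruments and a few sentences of text, with no new data collection. One outcome's claim becomes more modest.

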which women ultimately consent and participate in interventions. Study staff will have no contact information concerning the women who are reached by the peers, Centro Comunitario Juan Diego and The Resurrection Project, unless women contact study staff directly. Peers, Centro Comunitario Juan Diego and The Resurrection Project will not give any contact information to [name] and her team.

Interested women who have received the recruitment flyers, will contact UIC student/staff who will record women's contact information, screen them for eligibility, and obtain scheduling information for the Intervention sessions. We will ask each participant at time of recruitment/enrollment what language they prefer. Three 2-3 hour Workshop Sessions will then be scheduled for three consecutive weeks and held accordingly. For the Phase 3/Intervention, women will be informed that the sessions and workshops will be a "closed" group format. Once a woman agree to participate and enrolled in one of the 3 consecutive sessions, she cannot change or switch to another group's session.

With regard to interventions, once we have at least recruited 6-8 women per session, Centro Comunitario Juan Diego and The Resurrection Project will determine a date and time for use of conference room and fits within recruited women's schedules and begin the scheduling process. Once a date and time has been confirmed, UIC staff [Appendix P], will contact women two days prior to the session/s to remind them and reschedule, as needed. We will hold 5 – 9 sessions at each participating site for three consecutive weeks until we reach the targeted 150 Latina women.

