Six months after participation in Session 3, participants will be asked to complete Survey 3, which will take about 20-30 minutes. Survey 3 will be administered or in person at Centro Comunitario Juan Diego or The Resurrection Project sites. The reminder script has been modified to include scheduling calls, including for Survey 3 as well as the focus groups. Survey 3 will collect information related to information related to volunteerism history, social interactions, breast cancer beliefs (cultural beliefs, perceived risks, norms and social interactions concerning breast cancer) and breast cancer screening since Survey 1. For participants were in Cohort 1 (who completed participation before approved consent addendum), they will be contacted by phone up to 3 times with a script including consent addendum information to be given that information, wherein they can elect to be notified about future studies, if they are interested. If they are not interested, their data will be eliminated from this file. For cohorts 2-15, after the participant completes the final/third survey, her data will be eliminated from this file, if she chooses not to be contacted for future studies. If she chooses to be contacted for future studies, her information name and phone number (nothing else) will be kept and it will be recorded that she has completed participation, but is willing to be contacted in the future. Subsequently, each time she is contacted, this file will be updated to include a summary of the call. During each call, UIC staff will query the woman about her interest in being contacted in the future. If she chooses not to be contacted from future studies, her name and phone number will be eliminated from this contact log. If she chooses to be contacted for future studies, her name and phone number will remain in the contact log. Participants’ contact information will be kept until after participants decide to stop active participation or 5-7 years after the study is completed.

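### Phase 6a clusters its models by cohort with few cohorts and no small-sample correction named, and its power statement leaves the cohort clustering out

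*Combined protocol and SAP*

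**What the plan says.** Section 9.0 (Phase 6), repeated in sections 6.2 and 6.4, sets out Phase 6a as follows.

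- **Model:** "we will conduct Generalized Estimating Equation models with main effects (Study arm, time) and interaction terms (study arm*time"). Civic engagement intention, which was not measured repeatedly, gets a logistic regression.
- **Clustering:** "We will cluster by cohort/group and adjust for demographic covariates in all models".
- **Power basis:** the sample is "among 100 Latinas (assuming maximum attrition, given current attrition rates"), and the only correlation named is "across nested surveys (ICC = 0.0-0.5"). Power is 0.80 with a two-tailed test at .05.
- **Power result:** "we would be able to detect a medium-sized effect for a study arm*time interaction effect". No number and no effect-size metric is given.

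On the number of clusters, section 6.2 (Phase 3) says "We will hold 5 – 9 sessions at each participating site", and sections 1.0 and 3.0 put 5–8 recruited women in each. The groups are closed. Section 6.2 also numbers the cohorts: "For cohorts 2-15, after the participant completes the final/third survey". It does not say whether 15 is the total or the count per site.

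Section 12.1 calls Phase 6 a pilot, and section 6.2 calls the Phase 6a analyses secondary.

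**The concern.** There are two gaps, and both concern the cohort as a unit.

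1. **Size of the test.** A cluster-robust (sandwich) variance is justified as the number of clusters grows. With one to two dozen clusters, the uncorrected version referred to a normal distribution tends to be too small. The plan clusters on cohort but does not say how the variance is computed or what reference distribution is used. If a default is taken, the arm-by-time tests for Aim 6a reject more often than the stated 5% when there is no effect.

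2. **Power.** The model allows for cohort and the power statement does not. Its ICC of 0.0–0.5 refers to surveys within women: section 9.0 uses the same range for the Phase 3 psychosocial model, which has two levels only, surveys and participants. No cohort ICC, design effect or group count enters the power statement.

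**Working it through.** **Inputs.** From section 9.0: N = 100, two-sided 0.05, power 0.80, survey ICC (ρ) 0.0–0.5. Assumed: 50 women per arm, and a cohort ICC of *change* between 0 and 0.10. The documents give no cohort ICC.

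**How many groups?** I read the 5–9 sessions per site as 5–9 closed groups, so 10–18 over two sites. Other figures do not agree with this:
- 9 × 8 = 72, below the 75 women planned per site.
- 150/8 = 18.75 and 150/5 = 30, so 150 women need 19–30 groups.
- The 240 enrolled women (sections 3.0 and 5.0) need 240/8 = 30 to 240/5 = 48 groups.
- 15 cohorts hold 15 × 5 = 75 to 15 × 8 = 120 women.
- 10 groups hold at most 80 women, fewer than the 100 in the power statement, so 10 is an outer bound.

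I therefore show K = 10 to 30 groups.

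**Type I error of the arm-by-time test.** Simulated trials had N = 100, three surveys, ρ = 0.5, a continuous outcome, four covariates, an independence working correlation and the variance clustered on cohort, with 1,500–2,000 runs per setting. The ranges cover the settings run, up to a cohort ICC of 0.10.

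| Groups | Uncorrected sandwich, z | Uncorrected sandwich, t (K−2 df) | Mancl–DeRouen-type sandwich, t (K−2 df) |
|---|---|---|---|
| 10 | 11.7–11.8% | 6.9–7.3% | 3.3–3.4% |
| 14 | 8.3–9.1% | 5.5–6.4% | 2.8–3.5% |
| 18 | 8.1–8.7% | 6.0–6.5% | 3.5–3.9% |
| 30 | 6.7–6.8% | 5.7–5.9% | 4.2–4.5% |

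Further runs of the uncorrected z-test gave 12–13% (10 groups), 10–11% (15), 9% (18) and 7% (30), with the cohort ICC at or near 0. Another 3,000 trials with 15 cohorts of 5–8 gave 8.9–9.5% over cohort ICC 0–0.10. An exchangeable GEE without covariates (400 runs, cohort ICC 0.05) gave 10.8% at K = 10 and 7.3% at K = 18, with a Monte Carlo standard error of √(0.0725 × 0.9275/400) = 1.3 points for the latter. The inflation comes from the small number of clusters and does not depend on the assumed cohort ICC. The logistic model was not simulated.

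**Detectable effect, first without cohorts.** For the T1-to-T3 difference in change, in SD units,

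MDE = 2.80 × √(4(1−ρ)/50).

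At ρ = 0.5 this is 2.80 × √0.04 = 0.56. At ρ = 0 it is 2.80 × √0.08 = 0.79. As Cohen's f over three surveys, the same inputs give 0.13 and 0.18. The plan's own figure cannot be reproduced, because it is only a label.

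**Then with cohorts.** Take group size m = 100/K after attrition, design effect DE = 1 + (m−1) × ICC, multiply the MDE by √DE, and replace the normal reference by a noncentral t on K−2 df. At ρ = 0.5:

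| K | m | MDE, ICC 0 | DE at ICC 0.05 | MDE, ICC 0.05 | MDE, ICC 0.10 |
|---|---|---|---|---|---|
| 10 | 10.0 | 0.64 | 1.45 | 0.77 | 0.88 |
| 15 | 6.7 | 0.61 | 1.28 | 0.69 | 0.76 |
| 18 | 5.6 | 0.60 | 1.23 | 0.66 | 0.72 |
| 30 | 3.3 | 0.58 | 1.12 | 0.61 | 0.65 |

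Example: K = 10, ICC 0.05 gives 0.64 × √1.45 = 0.77.

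**The case against.** The strongest objections, and what stands of each:

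- **The label may be right.** A reader might infer that the claim of a medium effect is wrong. The documents do not support that. They give no metric, and on Cohen's f the unclustered values of 0.13–0.18 rise to at most about 0.25, the conventional medium value, even with a design effect of 1.9 (before any t correction). What can be said is that the statement omits a source of variation that the model includes, and that it cannot be checked as written. This objection stands.
- **Uncorrected errors are inferred from silence.** A reader might also infer that the plan has chosen standard errors that are too small. It has not chosen any. It names no estimator, working correlation or reference distribution, so the type I error figures are conditional on the default. This stands too, and it is a reason to specify the method.
- **A cohort effect that is constant over time cancels from arm-by-time.** Correct: only cohort differences in *change* cost power there. The cohort ICC above must be read in that sense. Nothing cancels for civic engagement intention, which was not measured repeatedly.
- **Recruited group sizes overstate the design effect.** Also correct. A recruited size of 6.5 scaled from 150 to 100 women gives m = 4.3, and from 240 to 100 gives m = 2.7. At ICC 0.05 the MDE then grows by about 8% and 4% before the t reference. The table uses 100/K for this reason.
- **The group count is uncertain.** It is, and at 30 groups both problems shrink. Neither disappears: type I error is still about 7%.

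**Conclusion.** The point holds as a gap in specification with a measurable risk. If the uncorrected sandwich z-test is applied at cohort level, type I error is about 9–13% with 10–18 groups and about 7% with 30, even at cohort ICC 0. This rests on N = 100, a continuous outcome and the default being used.

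The power statement omits cohort clustering, so on the change-score scale at survey ICC 0.5 the detectable effect is larger than the 0.56 SD that independent women would give. With a t reference it is 0.60–0.64 SD at cohort ICC 0 and 0.66–0.77 SD at cohort ICC 0.05, for 18 to 10 groups; with 30 groups it is 0.58 and 0.61 SD. The ICC of 0.05 is an assumption.

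Priority is low to moderate. The secondary and pilot status limits the consequence, though it does not change the error rate of a test run at .05 or the meaning of a stated 80% power. Nothing here touches a larger limitation: each arm is delivered at one site, so arm and site are confounded, and no cohort-level variance correction removes that.

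**What to change.** In section 9.0 (Phase 6), and where the text recurs in sections 6.2 and 6.4:

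1. State that the clustering unit is the cohort. Prespecify a small-sample-corrected sandwich variance (for example Mancl–DeRouen or Kauermann–Carroll) with a t reference on about (cohorts minus 2) degrees of freedom, for the GEE models and for the clustered logistic model.
2. Give the actual number of cohorts by site, and reconcile 5–9 groups per site, cohorts numbered to 15, and groups of 5–8 with 150 completing and 240 enrolled women.
3. Restate the detectable effect with its metric, a number, the group count, the group size after attrition and a range for the cohort ICC of change (for example 0–0.10, labelled as an assumption).

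The cost is a few sentences and a software option. The downside is slightly wider intervals, a mildly conservative test (about 3–4% in the simulations with 10–18 groups) and a less favourable stated effect. A t reference with the uncorrected variance is simpler, but it left type I error at about 5.5–7.3% over 10–18 groups.
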